##### **Secondary Efficacy endpoints:**

- Objective response rate

The ORR is the proportion of subjects achieving a best overall response of confirmed partial or complete response (irPR + irCR), according to irRECIST ([Appendix 1](#)) from first dose date until disease progression/recurrence. Subjects who do not have a tumor response assessment for any reason will be considered nonresponders and will be included in the denominator when calculating the response rate.

- Duration of response

Duration of response is defined as the time from the date of first documented confirmed irCR/irPR until the first documentation of confirmed disease progression or death, whichever comes first.

- Progression-free survival

Progressive-free survival is defined as the time from first dose date to the date of the first documentation of confirmed disease progression or death (whichever occurs first) using irRECIST. The censoring rule for events will be defined in the SAP.

- Disease control rate

The DCR is the proportion of subjects achieving irPR + irCR + irSD from first dose date until disease progression/recurrence.

- Clinical benefit rate

The CBR is the proportion of subjects achieving irPR + irCR + irSD [lasting at least 24 weeks] from first dose date until disease progression/recurrence.

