5.1.2 Secondary Endpoint(s)

Secondary Efficacy Endpoints:

- Objective response rate (ORR)

The ORR is the proportion of patients achieving a best overall response (BOR) of confirmed partial or complete response (irPR + irCR), according to the irRECIST (Section 13.2) from first dose date until disease progression/recurrence. Subjects who do not have a tumor response assessment for any reason will be considered nonresponders and will be included in the denominator when calculating the response rate.

- Duration of response (DOR)

The DOR is defined as the time from the date of first documented confirmed irCR/irPR until the first documentation of confirmed disease progression or death, whichever comes first.

- Progression-free survival (PFS)

The PFS is defined as the time from first dose date to the date of the first documentation of confirmed disease progression or death (whichever occurs first) using irRECIST. The PFS is also defined as the event that a subject is alive without confirmed disease progression at a specific evaluation time point. The censoring rule for events will be defined in the SAP.

- Disease control rate (DCR)

The DCR is the proportion of patients achieving irPR + irCR + irSD from first dose date until disease progression/recurrence.

- Clinical benefit rate (CBR)

The CBR is the proportion of patients achieving irPR + irCR + durable irSD [lasting at least 24 weeks] from first dose date until disease progression/recurrence.

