5.4.1 Efficacy Analyses According to immune-related RECIST (irRECIST)

Tumor assessments and overall response to the treatment according to irRECIST are presented in Section 13.2. The confirmation of progressive disease (irPD) is required at least 4 weeks after the initial irPD. If irPD at two consecutive tumor assessment visits with less than 4 weeks, the additional confirmation of irPD visit is required. If irPD is confirmed, the documented start date of irPD is determined as follows:

1. The date of the initial irPD if it is confirmed on consecutive tumor assessment visits.
2. The date of the second irPD if the initial irPD is confirmed not on consecutive tumor assessment visits.

The best overall response (BOR) is defined as follows:

- **irCR**

To achieve BOR of irCR, irCR must be observed at two consecutive tumor assessment visits with at least 4 weeks apart before the confirmed irPD, death, or end of study (whichever occurs first). If complete response at two consecutive tumor assessment visits with less than 4 weeks, the confirmation of irCR at the next assessment visit is required. The documented start date of irCR is defined as the date of the initial irCR.

- **irPR**

When BOR of irCR is not achieved, BOR of irPR can be achieved by that an initial irPR is confirmed by irPR or irCR at next consecutive visit (≥ 4 weeks after the first irPR response). If irPR or irCR happens at two consecutive tumor assessment visits within 4 weeks, the additional confirmation of irPR (irPR or irCR in a later visit) is needed for BOR of irPR. The documented start date of irPR is the date of the initial irPR.

- **irSD**

If the documented start date of irPD is not the first evaluable tumor assessment visit after the first dose of study drug and the BOR is not a confirmed irCR/irPR, then the BOR is stable disease (irSD) when the duration of irSD is no less than 5 weeks. The duration of irSD is defined as the time from the first dose date to the documented start date of irPD, death, or the last evaluable tumor assessment (whichever occurs first).

- **irPD**

If the documented start date of irPD is the first evaluable tumor assessment visit after the first dose of study drug, then the BOR is irPD.

Table 1 listed general rules in the derivation of BOR with two consecutive tumor response results.

Table 1 Derivation of BOR with Two Consecutive Tumor Response Results

| Timepoint 1 Initial Response | Timepoint 2 Follow-up Response ≥ 4 weeks | BOR |

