The time to response (TTR) is defined as the elapsed time (weeks) from the first dose date to the documented start date of confirmed irCR/irPR according to irRECIST. The descriptive statistics for the TTR will be summarized by dose group for the patients with the BOR of confirmed irCR/irPR.

Duration of Response (DOR)

The duration of response (DOR) is defined as the time (months) from the documented start date of confirmed irCR/irPR according to irRECIST until the documented start date of irPD or death (whichever occurs first).

For subjects with the BOR of irCR/irPR who did not die and had no documented progression before the cut-off date for the end of the study, or before early discontinuation (including discontinuations due to toxicity, undocumented clinical progression, change of cancer treatment, or decreasing performance status), and who died or progressed after more than one missed visit, will be censored on the date of their last assessment with the BOR of irCR, irPR or irSD.

The descriptive statistics (median and its standard error, Q1 and Q3) for the DOR will be summarized by dose group for the patients with the BOR of confirmed irCR/irPR using Kaplan-Meier method.

Progression-Free Survival (PFS)

Progression-free survival is defined as alive without confirmed irPD using irRECIST at the end of study or certain evaluation time points such as 3 months, 6 months, etc. The time for PFS is defined as the elapsed time from first dose date to the documented start date of irPD or death (whichever occurs first).

In analysis of PFS, the censoring rule is as follows:

- Subjects who did not die and had no documented progression (confirmed irPD) before the cut-off date for the end of the study, or before early discontinuation (including discontinuations due to toxicity, undocumented clinical progression, change of cancer treatment, or decreasing performance status), PFS will be censored on the date of their last evaluable assessment.
- Subjects who died or progressed after more than one missed visit, or non-evaluable assessment, or a combination of two, PFS will be censored on the date of their last evaluable assessment before the death or progression.

The rate for PFS will be summarized by evaluation time point and dose group. The time curve and median of PFS will be estimated and reported by the Kaplan-Meier method.

Disease Control Rate (DCR)

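### SAP 5.4.1 does not say which response start date applies when irPR deepens to irCR: read literally it conflicts with the DOR definition in SAP 5.1.2 and the protocol, and nothing settles TTR

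*SAP*

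**What the plan says.** SAP 5.4.1 uses a documented start date as its working term and, for responses, defines it only inside the BOR categories.

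- Under irCR: "The documented start date of irCR is defined as the date of the initial irCR".
- Under irPR, the paragraph opens "When BOR of irCR is not achieved, BOR of irPR can be achieved by that an initial irPR is confirmed by irPR or irCR" and ends "The documented start date of irPR is the date of the initial irPR".

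The same section then defines TTR as the time "from the first dose date to the documented start date of confirmed irCR/irPR according to irRECIST", and DOR as the time "from the documented start date of confirmed irCR/irPR according to irRECIST until the documented start date of irPD or death". Neither sentence says which date to take when a subject has had both an irPR and an irCR.

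The endpoint definitions elsewhere are more specific for DOR. SAP 5.1.2: "The DOR is defined as the time from the date of first documented confirmed irCR/irPR until the first documentation of confirmed disease progression or death". Protocol 9.7.1.1: "Duration of response is defined as the time from the date of first documented confirmed irCR/irPR". Neither of those sections defines TTR. Protocol 9.7.1.7 describes how TTR is summarised and censored but gives no onset date, so the only definition of TTR is the one in SAP 5.4.1.

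SAP 5.4.2 analyses the modified RECIST 1.1 versions of TTR and DOR in the same way.

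**The concern.** A programmer working from 5.4.1 alone finds one start date for a subject whose BOR is irCR, namely the first irCR. The irPR date appears only in the paragraph for subjects who did not reach irCR. A subject whose partial response deepens to a complete one would then be dated from the later scan.

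That sits badly with the SAP's own confirmation rule. The irPR paragraph and SAP Table 1 both count irPR followed by irCR at least 4 weeks later as a confirmed irPR. With irPR at week 6 and irCR at week 12, the subject already has a confirmed response with onset at week 6. If week 18 shows irCR again, the literal rule moves onset to week 12, so a better later scan removes six weeks of confirmed response.

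At stake are two secondary endpoints summarised by dose group. The subjects affected are those with the deepest response, and the shift makes their response look later and shorter. Escalation cohorts have 6 subjects, so a single responder could set a group's median.

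**Working it through.** The documents state no TTR or DOR figure, so there is nothing to reproduce. The check applies two readings of the start date to the same scan sequences.

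**Inputs from the documents**
- Scans every 6 weeks from Cycle 1 Day 1 (protocol 9.5.2).
- A response is confirmed by a scan at least 4 weeks later, and an irCR can confirm an irPR (SAP 5.4.1 and Table 1).
- An irPD confirmed at the next consecutive visit is dated at the first irPD (SAP 5.4.1).

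**Assumptions**
- First response at week 6; irPD at week 36, confirmed at week 42; no missed scans. These courses are illustrative: the documents give no expected response rate.
- One month = 30.4375 days. SAP 5.4.1 reports DOR in months but gives no conversion.

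**Formulas**
- TTR (weeks) = onset week.
- DOR (weeks) = 36 − onset week; months = weeks × 7 / 30.4375.
- Reading A: onset is the start date of the final BOR category.
- Reading B: onset is the earliest irPR or irCR that is later confirmed.

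| Course | A: TTR | A: DOR | B: TTR | B: DOR |
|---|---|---|---|---|
| irPR wk 6, irCR from wk 12 | 12 wk | 36 − 12 = 24 wk (5.52 mo) | 6 wk | 36 − 6 = 30 wk (6.90 mo) |
| irPR wk 6, irCR from wk 18 | 18 wk | 36 − 18 = 18 wk (4.14 mo) | 6 wk | 30 wk (6.90 mo) |
| irPR wk 6, irCR from wk 24 | 24 wk | 36 − 24 = 12 wk (2.76 mo) | 6 wk | 30 wk (6.90 mo) |
| irPR only, from wk 6 | 6 wk | 30 wk (6.90 mo) | 6 wk | 30 wk (6.90 mo) |
| irCR at first scan, wk 6 | 6 wk | 30 wk (6.90 mo) | 6 wk | 30 wk (6.90 mo) |

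In general, *k* scan intervals between first irPR and first irCR add 6*k* weeks to TTR and remove 6*k* weeks from DOR under reading A. One interval is 6 × 7 / 30.4375 = 1.38 months.

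Under reading A, the subject who reaches irCR at week 12 has a DOR of 5.5 months. The subject who stays at irPR, with the same first-response and progression dates, has 6.9 months.

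**Mixed use.** If DOR follows SAP 5.1.2 (onset week 6) while TTR follows the literal 5.4.1 (onset week 12), the first course gives TTR 12 + DOR 30 = 42 weeks for a subject whose progression is dated week 36. The two endpoints would no longer share an onset.

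**Other endpoints.** PFS is 36 weeks in every row. ORR, DCR and CBR depend on the BOR category and, for stable disease, on its duration from first dose, so the choice of response onset does not enter.

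**The case against.** A reader might infer that the SAP definitely restarts the clock at irCR, that it has abandoned the protocol's *first*, and that the deepest responders will therefore be reported with later and shorter responses. The documents do not support that much.

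- No sentence restarts the clock. TTR and DOR run from a joint term, confirmed irCR/irPR; in those definitions BOR selects which subjects are summarised and appears in the censoring text, but is not stated to choose the onset date.
- The condition about irCR not being achieved governs the assignment of BOR irPR. The irPR start date stands in a later sentence that carries no condition of its own. Since an irCR may confirm an irPR, the sequence irPR, irCR, irCR contains a confirmed irPR dated at the first irPR.
- SAP 5.1.2 keeps the protocol's wording for DOR, and SAP section 7 says no changes to the planned analysis are applied. The omission of *first* is confined to 5.4.1. Under 5.1.2 the shift in DOR is zero.
- The protocol gives no start date for TTR, so the SAP cannot be said to depart from it there.
- The consequence is modest. Both endpoints are descriptive, no test or decision threshold uses them, and protocol 9.1.1.4 places RP2D selection after the last escalation subject completes Cycle 1, with clinical activity considered only as available.

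All of this stands as a limit on the claim. It does not remove the point. Section 5.4.1 is the operational text that will be programmed, its literal reading gives a different DOR from 5.1.2 for the same subject, and for TTR there is no second definition to appeal to.

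**Conclusion.** The point holds as an internal conflict and ambiguity, not as a settled restart rule. For DOR, the literal reading of SAP 5.4.1 conflicts with SAP 5.1.2 and protocol 9.7.1.1. For TTR, the onset date is undetermined when irPR is followed by confirmed irCR.

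Where the literal reading is applied, the shift is 6 weeks (1.38 months) per scan interval between first irPR and first irCR, lengthening TTR and shortening DOR. It affects only subjects with a confirmed irCR preceded by irPR. Those who stay at irPR, or whose first response is already irCR, are unchanged.

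This rests on taking the first documented confirmed response in 5.1.2 and the protocol to mean the irPR date, which is its natural sense. The week counts use assumed courses, and how many subjects would be affected cannot be estimated from the documents. With at most 40 subjects and descriptive secondary endpoints the practical reach is small. Still, the text can yield two different values for one subject, so it should be corrected before database lock.

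**What to change.** Add one sentence to SAP 5.4.1: for both TTR and DOR, response onset is the date of the earliest irPR or irCR that is later confirmed, regardless of whether the final BOR is irPR or irCR. State that the same rule, using PR and CR, applies to the modified RECIST 1.1 analyses under 5.4.2. This brings 5.4.1 into line with SAP 5.1.2 and protocol 9.7.1.1 and gives TTR the same onset as DOR.

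The cost is one sentence and the matching derivation; no new data are needed. Listing the first irCR date separately is optional and not part of the correction.

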|---------------------------------|--|--|
| irCR | irCR | irCR |
| irCR | irPR/irSD/irPD | irSD/irPR* |
| irPR | irPR/irCR | irPR |
| irPR | irSD | irSD |
| irPR | irPD | irSD |
| irSD | irSD | irSD |
| irSD | irPD | irSD, provided minimum irSD duration met |
| irPD | irPD | irPD |

*If an irCR is truly met at first time point, then any disease seen at a subsequent time point, even disease meeting irPR criteria relative to baseline, makes the disease irPD at that point (since disease must have reappeared after irCR). Best response would be irSD. However, sometimes 'irCR' may be claimed when subsequent scans suggest small lesions were likely still present and in fact the patient had irPR, not irCR at the first time point. Under these circumstances, the original irCR should be changed to irPR and the best response is irPR.

- **irNE**

The BOR will be irNE in the following scenarios:

- No evaluable tumor assessment
- Only one evaluable tumor assessment with the result of either irPD or irCR/irPR/irSD but the duration of irSD is less than 5 weeks.

- **Handling of Missing /Not Evaluable Tumor Assessments**

The following rules will be used to handle missing and/or not evaluable tumor assessments:

- One missing or not evaluable tumor assessment will be ignored if it is between two evaluable tumor assessments.
- All the missing and/or not evaluable tumor assessments will be ignored if they are the only ones in between two irPDs. In this case, the irPD is confirmed and the documented start date of irPD is the date of the first irPD.
- All the missing and/or not evaluable tumor assessments will be ignored if there is no evaluable tumor assessment after them.
- Two irCRs, two irPR, or irPR and irCR with two or more missing and/or not evaluable tumor assessments in between will result in not evaluable result, i.e., irNE.

Objective Response Rate (ORR)

The objective response rate (ORR) is the proportion of patients achieving a best overall response of confirmed irPR or irCR according to irRECIST from first dose date until disease progression, death, or end of study (whichever occurs first). Subjects who do not have a tumor response assessment for any reason will be considered nonresponders and will be included in the denominator when calculating the response rate. The count and percentage for the ORR will be summarized by dose group.

Time to Response (TTR)

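### SAP Table 1: the footnote's irPR exception is not limited to an irPR follow-up, so a re-read irCR followed by irSD or irPD can be scored two ways

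*SAP*

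**What the plan says.** SAP 5.4.1 derives the best overall response (BOR) in two ways: by text rules for each category, and by Table 1, which it introduces as general rules for two consecutive results at least 4 weeks apart.

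- **Text rule for irPR:** "BOR of irPR can be achieved by that an initial irPR is confirmed by irPR or irCR at next consecutive visit", at least 4 weeks after the first irPR.
- **Table 1, irPR rows:** confirmed, "irPR | irPR/irCR | irPR"; not confirmed, "irPR | irSD | irSD". A first irPR followed by irPD is also scored irSD.
- **Table 1, merged irCR row:** "irCR | irPR/irSD/irPD | irSD/irPR", with a footnote on the last cell.
- **Footnote, default:** if irCR was truly met, any disease seen later is irPD at that point. "Best response would be irSD".
- **Footnote, exception:** "sometimes 'irCR' may be claimed when subsequent scans suggest small lesions were likely still present", so that the first time point was in fact irPR. "Under these circumstances, the original irCR should be changed to irPR and the best response is irPR".
- **ORR:** it "is the proportion of patients achieving a best overall response of confirmed irPR or irCR according to irRECIST", and it is summarised by dose group.

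The irRECIST appendix (SAP 13.2) also requires an irPR to be confirmed at least 4 weeks later.

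**The concern.** The row covers three different follow-up results, but the exception gives one result for all of them. Re-reading the first scan as irPR settles what that scan showed. It does not settle whether the response was confirmed, which depends on the second scan. When the second scan is irSD or irPD, the re-read sequence is an unconfirmed irPR, and other parts of the same section score it irSD.

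Section 5.4.1 has no confirmation step apart from the BOR derivation, so reaching a BOR of irPR is how a response comes to be treated as confirmed. One programmer could follow the footnote and another the text rule, and they could report different ORRs from the same data. The same BOR selects subjects for TTR and DOR. It also feeds CBR, where irPR counts without the 24 weeks required of irSD. SAP 5.4.2 defines the BOR for modified RECIST 1.1 by analogy, so the ambiguity carries over.

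The trigger is a judgement made after seeing later scans, in an open-label trial with investigator-read tumor assessments (Protocol 9.4.6 and 9.5.2). Clinical activity, as available, is one of the guidelines for choosing the RP2D (Protocol 9.1.1.4).

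**Working it through.** The plan states no figure on this point. The check takes each sequence in the merged row through each branch of the footnote and compares the result with the rest of SAP 5.4.1.

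| First scan, as finally read | Follow-up | Footnote | Other rules in 5.4.1 | Agree? |
|---|---|---|---|---|
| true irCR | irPR | irSD | no competing rule | yes |
| true irCR | irSD | irSD | no competing rule | yes |
| true irCR | irPD | irSD | no competing rule | yes |
| re-read as irPR | irPR | irPR | irPR (confirmed) | yes |
| re-read as irPR | irSD | irPR | irSD | **no** |
| re-read as irPR | irPD | irPR | irSD | **no** |

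Two of the six combinations conflict.

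**Can these sequences occur?** irPR needs a fall of at least 30% from the baseline sum of diameters. irPD on target lesions needs a rise of at least 20% and at least 5 mm from nadir. A lesion too small to measure is entered as 5 mm (SAP 13.2). The lesion sizes below are assumed for illustration.

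- 10 → 5 → 8 mm: the first scan is (5 − 10)/10 = −50%, irPR. The second is (8 − 10)/10 = −20% from baseline and +3 mm from nadir, so irSD.
- 30 → 15 → 22 mm: the first scan is −50%. The second is (22 − 30)/30 = −27% from baseline, but +7 mm and 7/15 = +47% from nadir, so irPD.
- 50 → 10 → 36 mm: the first scan is −80%. The second is −28% from baseline, but +26 mm from nadir, so irPD.

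The irSD conflict therefore needs small-volume disease, which eligibility allows: one measurable lesion of 10 mm is enough (Protocol 9.3.1, criterion 8). The irPD conflict has no such limit.

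**Size.** One affected subject moves ORR by 1/n, taking all n subjects as the denominator:

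- dose group of 6: 1/6 = 16.7 points
- expansion cohort of 16 on its own: 1/16 = 6.25 points
- that cohort pooled with the 6 escalation subjects at the same dose: 1/22 = 4.5 points
- all 40 subjects: 1/40 = 2.5 points

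The SAP does not say whether escalation and expansion subjects at the RP2D form one dose group, so both figures are shown.

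**Other endpoints.** DCR does not change if the 5-week minimum for irSD is met, because irPR and irSD both count. On the planned schedule it is met: the first scan falls in week 6, after at least 5 weeks, and the follow-up is at least 4 weeks later, so at least 5 + 4 = 9 weeks have passed. The effect on ORR and CBR can only be upward. In DOR, a response followed at once by confirmed irPD would enter as a short duration.

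**The case against.** The strongest reply is that the SAP already settles the matter. ORR, TTR and DOR are defined on confirmed irPR or irCR, and so are the response components of DCR and CBR. The text rule requires confirmation, Table 1 is offered only as general rules, and once the first scan is relabelled irPR the existing irPR rows apply and give irSD.

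Much of this stands. A reader might infer that the footnote makes irPR the result for the whole row. It does not: its default is irSD, and irPR is a conditional exception. A reader might also infer that the SAP tells the analyst to count unconfirmed responses in ORR. No sentence says so, and the ORR definition says the opposite. The irCR-irPR sequence, once re-read, is a confirmed irPR and belongs in ORR. Nor can one say that such a subject would probably be the only responder at a dose, because neither document gives an expected response rate.

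The reply does not remove the conflict. The footnote states a result, irPR, for a row that expressly includes irSD and irPD follow-up, and nothing says that the irPR rows take precedence over it.

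**Conclusion.** Wrong as written, minor severity. When a first irCR is re-read as irPR and the follow-up is irSD or irPD, the footnote taken literally gives a BOR of irPR. That contradicts two rows of the same table, the text rule on confirmation and the ORR definition. The footnote's default branch and the re-read irCR-irPR sequence are sound.

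The consequence is a possible miscount, not a certain one. It needs a claimed irCR, a re-read to irPR, a follow-up of irSD or irPD, and a programmer who follows the footnote. The documents give no frequency for this; I judge it rare. ORR is a secondary, descriptive endpoint. The point is still worth correcting because one subject is 16.7 points in a dose group of six and the error in ORR runs in one direction only.

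**What to change.** Split the merged row of Table 1 into three:

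- **irCR then irPR, at least 4 weeks later:** irPR if the first time point is re-read as irPR and the re-read is documented before database lock; otherwise irSD. Attach the footnote's irPR exception to this row only.
- **irCR then irSD:** irSD, subject to the 5-week minimum.
- **irCR then irPD:** irSD, subject to the 5-week minimum.

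Add a sentence saying that a first irCR relabelled irPR and followed by irSD or irPD takes the existing irPR-irSD and irPR-irPD rows. Apply the same split to the modified RECIST 1.1 derivation in SAP 5.4.2.

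The cost is three table rows and one sentence in the SAP. No new data are needed, and compared with the footnote read literally, ORR can only stay the same or fall.
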